### **8.4.2. Early Termination from the Study**

At the time of early study termination/stopping study participation, if possible, an early termination visit should be conducted. The participant will be permanently discontinued both from the IP and from the study at that time.

If the participant withdraws consent for disclosure of future information, the sponsor will retain and continue to use any data collected before such a withdrawal of consent. If a participant withdraws from the study, he/she may request destruction of any samples taken and not tested, and the investigator must document this in the site study records.

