**11.1.7. Data Collection at Follow-Up**

As applicable, the following will be documented during the follow-up visit(s):

- Dates and times of extubation and discontinuation of mechanical ventilation
  - The duration of time on mechanical ventilation will be calculated
- Dates and times of reintubation and re-initiation of mechanical ventilation
- Whether or not the participant requires oxygen delivered by high-flow nasal cannula (heated, humidified oxygen delivered via reinforced nasal cannula at flow rates >20L/min with fraction of delivered oxygen  $\geq 0.5$ ), and if so the date and time of initiation of oxygen delivery by high-flow nasal cannula
- Whether or not the participant requires noninvasive positive pressure ventilation and if so, the date and time of initiation of noninvasive positive pressure ventilation
- Whether or not the participant progressed to ECMO, and if so, the date and time of initiation and (as applicable) completion of ECMO
- Whether or not the participant progressed to tracheostomy, and if so, the date and time of the tracheostomy procedure
- Whether or not the participant died, and if so, the date, time, and cause of death

[REDACTED]

[REDACTED]

[REDACTED]

[REDACTED]

[REDACTED]

[REDACTED]

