## 5.2. Sample Size and Power

The sample size of approximately 100 participants would provide 80% power to detect a treatment difference of 27% in proportion of participants alive and free of respiratory failure at Day 28. The sample size is computed assuming proportion of 50% for the placebo group and 77% for the brexanolone group using Chi-square test with a two-sided Type I error rate (alpha) of 0.05.

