#### 8.1.2. Visit Windows

Visit windows are defined in [Table 2](#). It is noted that certain specific endpoints might have slightly different analysis visit rules. If an endpoint will be analyzed using the visit windows, as specified in the corresponding sections of the applicable endpoints, all assessments within the window, regardless if the assessment is scheduled or unscheduled, will be included. A

participant's individual analysis visit window could potentially contain more than 1 visit. In the event of multiple visits falling within an analysis window, the latest data will be used.

The summary by analysis visit will use the "analyzed records" only – at most one per participant within each window. The data not flagged as the "analyzed record" will be included in listings. A visit that does not fall under any analysis window will remain in the database and will be included in the listings. The visit window does not apply to the baseline assessment.

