### 8.3.2. Analysis of Primary Efficacy Endpoint

The primary efficacy endpoint is the proportion of participants alive and free of respiratory failure at Visit 11 (Day 28  $\pm$  3 days).

- If a participant dies prior to Visit 11, the participant will be assigned a value of “no” for the primary endpoint.
- Participants discontinuing the study for reasons other than death and prior to Visit 11 will not be included in the primary analysis.

The difference in the proportions between brexanolone and placebo will be analyzed using the SAS procedure GENMOD. In this model, the proportion will be the response variable, and the predictor variables will be treatment arm and age group (<70 or  $\geq$ 70 years).

Participants will be analyzed according to their actual age group, regardless of the age group used for randomization purposes. The proportion will be directly modeled using the binomial distribution with identity link. The point estimate, confidence interval, and p-value for the difference in the fitted proportions will be obtained using the “LSMEANS” statement to

 Lack of endotracheal intubation, for purposes of the Primary Efficacy Endpoint, does not require a subsequent  $>48$  hour period of time without need for reintubation or noninvasive ventilation.

produce estimated treatment differences (ie, differences in proportions). A sample SAS code is as follows:

```
proc genmod data=indata;
  class trt01p agegr1;
  model aval = trt01p agegr1 / dist=binomial link=identity;
  lsmeans trt01p / diff cl;
run;
```

Please see Appendix D for a detailed breakdown of the Procedural terms used to identify subjects with lack of respiratory failure.

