### 8.3.3. Analysis of Key Secondary Efficacy Endpoint

The proportion of participants who died for any cause (all-cause mortality) by Visit 11 (Day  $28 \pm 3$  days) is the key secondary endpoint.

- If a participant dies prior to Visit 11, the participant will be assigned a value of “yes” for the key secondary endpoint
- Participants having Visit 11 (either in-person or via phone call) will be assigned a value of “no” for the key secondary endpoint
- Participants having follow-up assessments on/after Day 25 and known to be alive for those assessments and for whom Visit 11 was not performed will be assigned a value of “no” for the key secondary endpoint
- Participants with early study termination (ET) for reasons other than death and prior to Visit 11 will not be included in the primary analysis.

The difference in the proportions between brexanolone and placebo will be analyzed using the SAS procedure GENMOD. In this model, the proportion will be the response variable, and the predictor variables will be treatment arm and age group ( $<70$  or  $\geq 70$  years).

Participants will be analyzed according to their actual age group, regardless of the age group used for randomization purposes. The proportion will be directly modeled using the binomial distribution with identity link. The point estimate, confidence interval, and p-value for the difference in the fitted proportions will be obtained using the “LSMEANS” statement to produce estimated treatment differences (ie, differences in proportions). The sample SAS code presented in Section 8.3.2 will be adapted for this purpose.

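### For a participant with no Visit 11 but a known status on Day 25–31, SAP 8.3.2 excludes or fails to define the primary outcome, and the mortality rules in SAP 8.3.3 conflict

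*SAP*

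**What the plan says.** Both efficacy endpoints are read at Visit 11, Day 28 ± 3 days (SAP 8.3.2 and 8.3.3). SAP 8.3 adds that Day 28 means Visit 11 throughout the efficacy analyses.

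**Primary endpoint (SAP 8.3.2).** There are two rules. Death before Visit 11 is scored no. The other rule reads: "Participants discontinuing the study for reasons other than death and prior to Visit 11 will not be included in the primary analysis".

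**Mortality (SAP 8.3.3).** There are four bullets:

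1. Death before Visit 11 is scored yes.
2. A Visit 11, in person or by phone, is scored no.
3. Also scored no are "Participants having follow-up assessments on/after Day 25 and known to be alive for those assessments and for whom Visit 11 was not performed".
4. Early terminations before Visit 11 for reasons other than death are left out. The bullet says they are left out of the primary analysis, although the section concerns the key secondary endpoint.

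**Windows (SAP 8.1.2, Table 2).** Visit 11 has an analysis window of Day 25 to Day 31. Where windows are used, "all assessments within the window, regardless if the assessment is scheduled or unscheduled, will be included". The same sentence makes this conditional on the endpoint's own section calling for windows.

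**Principles.** SAP 4.1.3 adopts a treatment-policy strategy that uses every on-study observation for both endpoints. Protocol 13.2 says the primary method uses all available non-missing data. SAP 6.1.5 drops the tipping-point analyses.

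**The concern.** The primary analysis should use an outcome that was observed inside its own window. As written, 8.3.2 sets one group of such outcomes aside by rule and leaves another to the programmer. The neighbouring mortality section shows that the authors foresaw a missed Visit 11 and were content to use a Day 25 or later assessment instead.

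At stake is the primary estimate in a trial that stopped early, where single participants carry weight. Someone counted as alive for mortality might have no value for being alive and free of respiratory failure, and the choice would be made outside the plan. With the tipping-point analyses dropped, no planned missing-data sensitivity analysis would show the effect.

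The point is limited to participants whose status in the window is already in the database. It does not concern participants whose Day 28 outcome is unknown.

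**Working it through.** **Step 1. The plan's own figure.** SAP 5.2 gives about 100 participants, 80% power and rates of 50% and 77%, "using Chi-square test with a two-sided Type I error rate (alpha) of 0.05". With p̄ = (0.50 + 0.77)/2 = 0.635:

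n per arm = [1.960·√(2·0.635·0.365) + 0.842·√(0.50·0.50 + 0.77·0.23)]² / 0.27² = 49 after rounding up, or 98 in total.

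At 50 per arm the power is 81.0%. The figure reproduces, and the sample size is not in dispute.

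**Step 2. The rules applied to each type of participant.**

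| Participant | Primary (8.3.2) | Mortality (8.3.3) |
|---|---|---|
| Dies before Visit 11 | No | Yes (bullet 1) |
| Has Visit 11 | Scored | No (bullet 2) |
| On study, Visit 11 missed, respiratory status recorded on Day 25–31, alive | No rule | No (bullet 3) |
| Leaves on Day 25–31 before Visit 11, after such an assessment | Excluded by rule | Bullet 3 scores no; bullet 4 excludes |
| Leaves before Day 25, no later record | Excluded | Excluded |

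The third and fourth rows are the problem. The third has an undefined primary outcome beside a defined mortality outcome. The fourth has an explicit primary exclusion beside a contradictory mortality rule.

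**Step 3. Does the window rule close the gap?** Not reliably. Table 2 would place a Day 25–31 record in Visit 11, but SAP 8.1.2 applies windows only where the endpoint's section says so. Section 8.3.2 repeats Day 28 ± 3 without invoking them. Section 8.3.3 uses the same ± 3 days and still needs its own Day 25 bullet, which suggests the window alone was not relied on. For participants who discontinue, the exclusion is explicit whatever the windows say.

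**Step 4. Are the data collected?** Often, but not always. Protocol 11.1.7 lists "Dates and times of extubation and discontinuation of mechanical ventilation". It also lists reintubation, ECMO start and completion, and death. For high-flow oxygen and noninvasive ventilation it asks whether the participant requires the support and when it started, but not when it stopped. For those who leave, Protocol 8.4.2 says that, if possible, "an early termination visit should be conducted". Being known alive therefore does not by itself settle the primary endpoint.

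**Step 5. Size, by illustration.** The documents give neither the number affected nor the final arm sizes, so the arm sizes and responder counts below are assumptions. With s responders among n, dropping m participants of known status gives s/(n − m) if all were non-responders and (s − m)/(n − m) if all were responders.

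| Assumed arm | All kept | One non-responder dropped | One responder dropped |
|---|---|---|---|
| n = 20, s = 10 | 50.0% | 10/19 = 52.6% | 9/19 = 47.4% |
| n = 25, s = 19 | 76.0% | 19/24 = 79.2% | 18/24 = 75.0% |
| n = 50, s = 38 | 76.0% | 38/49 = 77.6% | 37/49 = 75.5% |

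Dropping two from the 20-per-arm case gives 10/18 = 55.6% or 8/18 = 44.4%, a shift of 5.6 points.

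The loss of power is minor. At the planned size and rates, losing 2% (98 participants) leaves 80.2%, and losing 5% (95) leaves 79.0%. The trial stopped early, so these are not its actual power.

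**The case against.** The best defence has four parts.

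- **The endpoints need different evidence.** Vital status needs only a contact; respiratory status needs a record of support in use. Some asymmetry is therefore reasonable. This stands, and it limits the remedy to records that document respiratory status. It does not justify excluding a participant who has such a record.
- **8.3.2 does not exclude participants still on study.** Its exclusion covers only those who discontinue, and one reading of Day 28 ± 3 with Table 2 would score the others from in-window data. This stands as far as it goes. A reader might infer that known outcomes in this group are certainly discarded. The text shows only that the treatment is undefined.
- **8.3.3 has nearly the same exclusion.** A reader might infer that someone leaving on Day 25–31 is scored for mortality and dropped from the primary. The documents do not support that clean split, because bullets 3 and 4 of 8.3.3 give opposite answers.
- **The case is probably uncommon.** Visit 11 may be done by phone and falls within a seven-day window. This stands, and the number affected could be zero.

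A reader might also infer that those affected are mostly still in hospital, so that respiratory support decides who is dropped and biases the result in a known direction. Nothing in the documents establishes who they are, how they divide between arms, or which way the estimate would move.

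**Conclusion.** The concern holds in a limited form. One group with a known in-window status is removed from the primary analysis by an explicit rule, and another has no primary scoring rule. Both sit badly with the estimand in SAP 4.1.3 and with Protocol 13.2. The readable entries of SAP 6.1 declare no departure from the non-missing-data sentence, although part of 6.1 is redacted. Separately, 8.3.3 contradicts itself for participants who leave after a Day 25 or later assessment.

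The size is unknown. One participant moves an arm's rate by 2.6 points under the assumption of 20 per arm at 50%, and by between 0.5 and 3.2 points in the other two cases shown (76.0% to 75.5%, and 76.0% to 79.2%). The direction depends on whether that participant was a responder. These figures show sensitivity; they are not an estimate of bias. The reason to act is that the primary outcome should be fully defined before unblinding, and here that costs little.

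**What to change.** Make these changes before database lock. If lock has passed, SAP section 2 requires a change to be documented and discussed in the clinical study report.

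1. **SAP 8.3.2.** Keep the death rule first. Then state that when Visit 11 was not performed, including after study discontinuation on or after Day 25, a participant with a Study Day 25–31 record documenting vital status and current respiratory support is scored from that record. Use the latest such record in the window, consistent with SAP 8.1.2. Limit the exclusion bullet to participants with no such record.
2. **Respiratory status.** State that high-flow oxygen or noninvasive ventilation is not taken to have ended on the strength of a start time alone.
3. **SAP 8.3.3.** Make bullets 3 and 4 mutually exclusive, and change the reference in bullet 4 from the primary to the key secondary analysis.
4. **Reporting.** Give per arm the number scored under the new rule, and the number scored for mortality but not for the primary endpoint. The second count also picks up anyone scored for mortality from a contact after Day 31, since bullet 3 has no upper day limit.

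The cost is a few sentences and a small derivation, with no new data. The downside is that a few participants would be scored from a Day 25–31 record rather than a formal Visit 11. The SAP already accepts this kind of substitution for mortality.

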## 5.3. Randomization

This is a randomized, double-blind, placebo-controlled study. Participants who meet the eligibility criteria will be randomized in a stratified manner based on age ( $<70$  or  $\geq 70$  years). Participants will be randomized in a 1:1 ratio within each stratum to receive brexanolone plus standard of care or placebo plus standard of care. Randomization will be performed centrally via an interactive response technology system. Randomization schedules will be generated by an independent statistician outside Sage.

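### Wald inference from the identity-link model can run modestly above 5% at about 40 to 60 participants with mid-range event rates; SAP 8.3.2 and 8.3.3 should use an age-stratified score method

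*SAP*

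**What the plan says.** SAP 5.2 gives the design basis: "The sample size of approximately 100 participants would provide 80% power to detect a treatment difference of 27" percentage points, "assuming proportion of 50% for the placebo group and 77% for the brexanolone group", and "using Chi-square test with a two-sided Type I error rate (alpha) of 0.05". SAP 5.3 fixes the allocation: "Participants will be randomized in a 1:1 ratio within each stratum", the strata being age under 70 and 70 or over.

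The analysis uses a different statistic. SAP 8.3.2 fits a binomial model with identity link on treatment and age group and states: "The point estimate, confidence interval, and p-value for the difference in the fitted proportions will be obtained using the" LSMEANS statement. The sample code requests "lsmeans trt01p / diff cl", with no exact, score or likelihood-ratio option. SAP 8.3.3 does the same for mortality: "The proportion will be directly modeled using the binomial distribution with identity link", and "The sample SAS code presented in Section 8.3.2 will be adapted for this purpose".

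SAP 2 and 6.1 say that the study is being stopped early because of recruitment. Several analyses were dropped, but this model was kept. Participants who leave before Visit 11 for reasons other than death are excluded from both analyses, which lowers the number further. The achieved number is not stated.

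**The concern.** The LSMEANS difference is tested and bounded with a Wald standard error and normal quantiles. Its variance is evaluated at the fitted proportions and not under the null, so in small samples the test tends to reject too often and the interval tends to be too short. The chi-square test used for sizing takes its variance under the null.

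The odds ratio, Kaplan-Meier and tipping-point analyses have been dropped (SAP 6.1.4, 6.1.5). One p-value and one interval per endpoint therefore carry most of the efficacy reading. If they are anti-conservative, the report overstates the evidence. A fallback for non-convergence would not help, because the issue arises in fits that converge.

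**Working it through.** **1. The plan's own figure.** Inputs from SAP 5.2: p0 = 0.50, p1 = 0.77, difference 0.27, two-sided alpha 0.05, power 80%. The mean rate is 0.635.

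n per arm = [1.960 × √(2 × 0.635 × 0.365) + 0.842 × √(0.50 × 0.50 + 0.77 × 0.23)]² / 0.27² = 1.884² / 0.0729 = 48.7, so 49 per arm and 98 in total. Exact chi-square power at 50 per arm is 81.3%. The stated 100 for 80% is reproduced.

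**2. Direction without the age term.** With n per arm and observed difference d, the unpooled (Wald) variance equals the pooled (chi-square) variance minus d²/(2n). With equal arms the Wald p-value can therefore never be the larger of the two.

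Illustration: 9/20 against 15/20, d = 0.30.
- Wald: variance (0.45 × 0.55 + 0.75 × 0.25)/20 = 0.02175, z = 0.30/0.1475 = 2.03, p = 0.042.
- Chi-square: variance 2 × 0.60 × 0.40/20 = 0.0240, z = 0.30/0.1549 = 1.94, p = 0.053.
- Check: 0.0240 − 0.30²/40 = 0.02175.

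**3. Exact size without the age term** (enumeration of all tables, null rates 30%, 40% and 50%):

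| Per arm | Wald | Chi-square |
|---|---|---|
| 15 | 5.7–6.7% | 4.6–5.5% |
| 20 | 6.9–8.1% | 4.3–5.3% |
| 25 | 6.3–6.5% | 5.4–6.5% |
| 30 | 5.2–5.8% | 4.9–5.2% |
| 50 | 5.3–5.7% | 5.0–5.7% |

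The value at 20 per arm is a local peak of a discrete distribution: Wald is 5.4–6.6% at 22 per arm and 5.5–6.0% at 23. At 25 per arm and a 50% rate both tests give 6.5%.

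**4. The planned age-adjusted model under the null.** Assumptions, since the documents give none: 25% aged 70 or over, arms split evenly within stratum, 15,000 trials per setting, maximum likelihood. Wald size is taken over clean fits only (converged, all fitted rates strictly between 0 and 1). The Wald range is for the standard error from observed and from expected information. After the slash is age-stratified CMH over all simulated trials with every age-by-arm cell filled. Entries are percentages. Simulation error is about √(0.05 × 0.95/15,000) = 0.18 points, somewhat more where few fits are clean.

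| Null rate, <70 / ≥70 | N=20 | N=30 | N=40 | N=50 | N=60 | N=100 |
|---|---|---|---|---|---|---|
| 50 / 50 | 4.5–5.0 / 4.8 | 6.0–6.2 / 4.6 | 6.9–7.3 / 4.6 | 6.4–6.7 / 5.2 | 5.6–5.8 / 5.5 | 5.4 / 5.3 |
| 40 / 40 | 3.9–4.6 / 4.3 | 5.7–5.9 / 4.6 | 6.3–6.7 / 4.4 | 5.7–5.9 / 5.2 | 5.4–5.7 / 4.9 | 5.4 / 5.1 |
| 30 / 50 | 3.0–3.7 / 4.4 | 4.9–5.4 / 4.7 | 6.1–6.3 / 5.1 | 6.2–6.4 / 5.4 | 5.9–6.0 / 4.9 | 5.5 / 4.9 |
| 40 / 60 | 3.8–4.3 / 4.2 | 5.2–5.6 / 4.5 | 6.2–6.7 / 4.7 | 5.8–6.1 / 5.2 | 5.4–5.6 / 4.8 | 5.4 / 5.1 |
| 50 / 30 | 3.9–4.3 / 4.5 | 4.9–5.3 / 5.0 | 5.2–5.7 / 4.4 | 5.1–5.7 / 5.3 | 5.0–5.3 / 5.1 | 5.4–5.6 / 5.1 |
| 40 / 20 | 2.5–3.0 / 4.4 | 3.5–3.8 / 4.9 | 3.6–4.3 / 4.8 | 3.7–4.3 / 5.0 | 3.9–4.5 / 5.0 | 4.4–4.8 / 4.8 |

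Over the first five rows at N = 40 to 60 (15 cells, averaged before rounding), Wald averages 86.98/15 = 5.8% with observed information and 91.78/15 = 6.1% with expected information. CMH averages 74.52/15 = 5.0%.

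A separate simulation used permuted blocks of 4, null rates of 55%/35% or 30%/60% (<70/≥70) and 36 to 60 participants. It gave 5.5–6.7% (average about 6.2%) for Wald and 4.4–5.8% (average about 4.9%) for CMH.

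**5. Mechanism.** The ratio of model standard error to empirical standard deviation is about 0.96 to 0.99 in most settings at N = 40 to 60. It is 1.04 to 1.11 at N = 20, and 1.04 to 1.08 in the 40/20 setting at N = 30 to 60. There the clean-fit condition screens out sparse tables: the clean share is only 45–75% at N = 20.

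**6. Cost in power.** Exact, 50% against 77%, 25 per arm: Wald 55.6%, chi-square 54.2%.

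**The case against.** A reader might infer that both tests exceed 5% at whatever number was reached. The documents do not support that. Step 4 shows clean-fit size at or below 5% at N = 20 in every setting, and at every N shown when the older stratum has a 20% rate. For mortality the protocol's introduction says only that up to about half of critical-care patients do not survive, and no design rate is given. At a 20% event rate, with 0% and 100% arms set aside, the unadjusted Wald test has exact size 2.7% at 10 per arm, 2.9% at 15 and 5.3% at 20. The direction for mortality is open.

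A reader might also infer that a stated error rate is breached. The 0.05 appears only in the sample-size section, for a chi-square test. Neither 8.3.2 nor 8.3.3 attaches a level to its p-value, and no alpha is stated anywhere for mortality. That is a gap in the SAP, not a broken promise.

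The exact unadjusted figures partly reflect discreteness, do not describe the age-adjusted model, and barely separate the methods at 25 per arm. All of this stands, as does the point that the excess is small: at most about 2.3 points in the adjusted simulation.

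Finally, the planned model adjusts for the randomization factor and directly estimates the SAP's summary measure, a difference in response probabilities. That is a reason to keep its estimate. It is not a reason to rely on its Wald interval, because a stratified score method targets the same type of measure and uses the same factor.

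**Conclusion.** The point holds in conditional form. Given a clean fit, the planned Wald inference can be modestly anti-conservative: about 5.5% to 7% at roughly 40 to 60 participants with mid-range rates, against about 5% on average for age-stratified CMH. Mid-range is the plan's own setting for the primary endpoint, with 50% assumed on placebo. The excess is largest near 40 participants, has largely faded by 60, and is about half a point or less at 100.

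It does not hold at about 20 participants or with a low-rate age stratum, and nothing is established for mortality. The result rests on assumed totals of 20 to 60, about 25% aged 70 or over, and the null rates tabulated, because the documents give none of these after early termination.

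**What to change.** In SAP 8.3.2 and 8.3.3:
- State the two-sided alpha of 0.05 and the 95% confidence level for each test.
- Take the p-value and the 95% interval for the risk difference from one score method stratified by age (<70, ≥70): the stratified Miettinen-Nurminen interval, with CMH as the matching test. Specify Mantel-Haenszel stratum weights, so that at zero difference the interval and the test rest on the same statistic and cannot disagree.
- Report the identity-link estimate as supportive.

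The cost is SAP wording and standard SAS code. P-values become slightly less favourable; power for 50% against 77% at 25 per arm falls from about 56% to 54%. A stratum with an empty arm contributes nothing, so the SAP should say that such a stratum will be reported if it occurs.
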